The psychometric properties of the WOMAC have been extensively studied in a number of publications. The original publication by Bellemy (Bellemy et al., 1988) found a high level of responsiveness, Chronbach's alpha greater than 0.85, acceptable validity testing against multiple other scales including the Lequesne, Bradburn, and Doyle, and superior efficiency over other measures.

The psychometric properties of the WOMET in a population of patients with degenerative meniscal tears were recently published (Sihvonen et al., 2012). Test-retest reliability 95% limits of agreement were 20.1 and -20.11 as a percentage of normal score. Cronbach alpha score for total WOMAC was 0.91 and was greater than 0.7 for all domains. Floor and ceiling effects were less than 30%. The WOMET was significantly correlated to the Lysholm knee score ($r=0.558$, $p<0.001$) and the 15-D scale ($r=0.311$, $p=0.002$). Construct validity and responsiveness were also established.

[figure not shown]
Preoperative baseline WOMET and WOMAC scores were compared to postoperative values at one year. Subjects were also defined according to age (greater than 50 or younger), BMI, OA grade (K-L classification), meniscal tear type (complex or simple), smoking history (yes/no), psychiatric diagnosis (yes/no), and PTSD diagnosis (yes/no). Two orthopaedic surgeons evaluated the xrays and MRI films independently with discrepancy resolved through consensus. Other variables were identified through detailed chart review of diagnoses and parameters. Forty-five subjects completed one-year followup and were available for analysis. WOMAC and WOMET scores improved significantly in the entire cohort at one year ($p<0.0001$). Patients with

OA grade 0-1 had greater improvements than those with grade 2-3. Mean differences in WOMET and WOMAC scores overall (95% CI, p-value) in 45 subjects at 1 year were 354 (224-483; $p < 0.0001$) and 561 (407-714, $p < 0.0001$); respectively. Subgroup analysis based on lower OA grade (0 and 1) revealed mean differences in WOMET and WOMAC scores of 456 (290-621, $p < 0.0001$) and 656 (466-845, $p < 0.0001$) at 1 year; respectively. Chronicity of symptoms and tear type had no effect on outcomes. Other variables such as age, BMI, type of meniscus tear, smoking history, and psychiatric diagnosis had no significant impact on the results.

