This preliminary study gave us experience recruiting and following arthroscopic meniscectomy patients and experience with the WOMAC and WOMET, the primary outcome measures for the current study. We defined mean and standard deviation scores in our meniscectomy patient population that allow us to perform a power analysis for our proposed study. Furthermore, we defined a covariate, radiographic severity of osteoarthritis, that appears to have an effect on outcomes. This study lays a good foundation for the current study that is being proposed. It strongly suggests the need for a prospective study on arthroscopic meniscectomy for degenerative tears that has a control group, as the improvement in the arthroscopic meniscectomy patient population we observed in our pilot study is comparable in magnitude to the improvements seen after placebo surgery (Moseley et al., 2002) and physical therapy (Kirkley et al., 2008) interventions for knee osteoarthritis.

Effects of Meniscectomy on Gait and Functional Measures

We have recently completed a study with gait analysis on patients who have had arthroscopic medial meniscectomy (Netravali et al., 2010). The menisci are known to influence the transverse plane movements (anterior-posterior (AP) translation and internal-external (IE) rotation) of the knee during walking. In that study we sought to determine the influence of partial medial meniscectomy on the kinematics and kinetics of the knee during the stance phase of gait by testing the differences in AP translation and IE rotation, knee flexion range of movement, peak flexion and extension moments, and adduction moments between the meniscectomized knees and the healthy contralateral knees in ten patients ranging from 45 to 79 years of age.

Figures 1 and 2: Kinematic and kinetic differences between knees with and without posterior medial meniscectomy (PMM) (Figures from Netravali et al., J Biomechanics 2010)

We found that the primary kinematic difference was a significantly greater external rotation of the tibia through the stance phase of gait with eight of ten subjects demonstrating this pattern. Limbs that had undergone posterior medial meniscectomy also had lower peak flexion and extension moments compared to the normal limbs. We interpreted this result as resulting in changes of tibio-femoral contact during walking, which could be a mechanism for initiating the process of post-meniscectomy osteoarthritis.

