Imaging of muscle cross sectional area: Muscle cross sectional area measurement can provide additional information regarding the functional consequences of meniscectomy. We will image the thigh of patients at enrollment, and at two-year follow up to determine if patients undergoing meniscectomy vs. lavage have greater changes in muscle cross sectional area. Images will be obtained using a rapid axial thigh scan with IDEAL fat/water separation using a 3D spoiled gradient echo sequence. The data will have 1 mm in-plane resolution and 5 mm slice thickness. Acquisition time will be approximately 2 minutes. Muscle cross sectional area will then be determined as previously described {Walton 1997}.

Research Design and Methods

In this study we propose a prospective, randomized, blinded, and controlled clinical trial of arthroscopic meniscectomy in patients between the ages of 45 and 70 with degenerative meniscus tears.

Patient Selection:

Subjects will be recruited from the orthopedic clinic at the VA Palo Alto Healthcare System. Eligible subjects will meet the following inclusion criteria:

1. Age between 45 and 70 years
2. Degenerative meniscus tear as seen by a standard clinical MRI scan
3. A complaint of “mechanical symptoms” which would include popping, catching, or locking of the knee
4. Persistent symptoms for a minimum of three months despite conservative management including anti-inflammatory medications and physical therapy
5. Patient is enrolled for arthroscopic meniscectomy
6. The subject agrees to study follow-up schedule and signs informed consent.

The following exclusion criteria will be enforced:

1. Radiographic osteoarthritis of the knee in any compartment that is greater than KL grade 2
2. Prior knee arthroscopy within two years of study enrollment
3. Unable to have an MRI scan
4. Does not agree to participate

General Study Plan:

Patients who satisfy the inclusion and exclusion criteria and are scheduled for arthroscopic meniscectomy will be approached during their preoperative visit to participate in the study. They will be enrolled when they give informed consent.

Preoperative study related evaluation:

Prior to undergoing surgery, the patient will have the following evaluations:

1. The patient will fill out the WOMET (Kirkley et al., 2007) and WOMAC (Bellamy et al., 1988) surveys.
2. The patient will undergo a gait analysis
3. The patient will have MRI of the knee and thigh.

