4. The patient will have standing radiographs of the affected knee.

Evaluation at the time of surgery:

At the time of surgery, the patient will be randomized to treatment with either an arthroscopic partial meniscectomy or arthroscopic lavage. Randomization will be done by opening a sealed envelope in the operating room prior to the procedure. To ensure balanced numbers in the two surgical conditions, especially at the time of the interim look, randomization will be done by permuted blocks of size 10, thereby ensuring 5 patients in each group at every increment of 10 enrollees.

Upon initiation of the surgery, a sample of synovial tissue and synovial fluid will be obtained for biochemical analysis. During the operation, the status of the knee joint will be documented. This will include classifying the degree of chondromalacia according to the Outerbridge classification in all three compartments of the knee, and documenting the geometry and pattern of meniscus tear type. Video and photographs will be taken to assist with this documentation and will be stored in a secure manner.

During the operation, the meniscus will be carefully probed. If a large unstable flap of tissue can be displaced into the articulation (such as a bucket handle tear) this torn fragment will be debrided regardless of the result of randomization. This will be done as it is widely believed that it is inappropriate to leave such an unstable tear untreated. Any other tear types that do not result in an unstable flap that can be displaced into the articulation will be either retained or debrided, depending on the result of randomization.

All postoperative contact from this point forward will be made by study personnel who were not involved in the surgery and who do not have knowledge of the randomization result.

At 2 weeks and 6 weeks:

The patient will have regularly scheduled clinic visits at 2 and 6 weeks that are not a part of the study but are just a part of the routine postoperative care of knee arthroscopy patients. Postoperative care as deemed necessary by the treating physician will be provided and could include pain and/or anti-inflammatory medications. Physical therapy is rarely needed. All provided treatments will be recorded in the chart.

Evaluation at 3 months:

1. The patient will fill out WOMET and WOMAC surveys.
2. The patient will undergo gait analysis.
3. The patient will have an MRI of the knee

Evaluation at 6 months:

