Hypothesis 1a: The 12 month WOMAC score will be our primary outcome measure for this aim and the endpoint for this power analysis. The WOMAC is a validated osteoarthritis outcome tool that is widely used to assess the severity of pain, stiffness, and function due to osteoarthritis. A 20% improvement in the total WOMAC score is considered to be clinically important (Kirkley et al., 2008). In a preliminary study, we evaluated a cohort of 45 patients undergoing arthroscopy and meniscectomy at our institution (Mirza et al., 2010). We found a mean preoperative WOMAC score of 1296 with a standard deviation of 392. Twenty percent of the mean baseline score of 1296 is 260.

To ensure patient safety, we are incorporating in our analysis an interim look at the results by the DSMB to ensure that one group does not have dramatically superior results to another group. In addition, the DSMB will assess subject attrition rates by group and adverse events.

This will take place after 25% of the total planned number of subjects complete the study. This analysis will include assessment of drop-out rates and adverse events as well.

Setting the experiment-wide alpha at 0.05 and power at 80%, sample sizes of 37 and 37 achieve 81% power to detect a difference of 260 between the group means with standard deviations of 392 and 392 at a significance level (alpha) of 0.05 using a two-sided independent sample t-test. These results assume that 2 sequential tests are made using the O'Brien-Fleming spending function to determine the test boundaries. The interim look will thus take place when the first 20 subjects (25% of the total 74) complete the 12 month assessment. The analysis assumes that we will stop the trial if either condition is superior. The critical t-value will at the interim look will be +/- 4.3326. If the trial continues, the final analysis will use a critical t-value of 1.96. Sensitivity analyses will be conducted with t-tests on the baseline-to-12-month change scores.

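### KL grade, the covariate the sponsor's pilot singled out, is left out of the primary 12-month WOMAC comparison; one prespecified term would give a modest, nearly free gain in precision

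*Combined protocol and SAP*

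**What the plan says.** - **Eligibility** (Patient Selection, exclusion criterion 1). The only radiographic limit is an upper one: "Radiographic osteoarthritis of the knee in any compartment that is greater than KL grade 2". KL 0, 1 and 2 are all eligible.
- **Pilot** (Preliminary Studies). In 45 patients followed to one year, those with "OA grade 0-1 had greater improvements than those with grade 2-3". From this the sponsor concludes: "we defined a covariate, radiographic severity of osteoarthritis, that appears to have an effect on outcomes". Age, BMI, tear type, smoking and psychiatric diagnosis had no significant impact.
- **Timing** (Preoperative study related evaluation). "The patient will have standing radiographs of the affected knee" before surgery, so the grade can be known before the envelope is opened.
- **Allocation** (Evaluation at the time of surgery). "randomization will be done by permuted blocks of size 10, thereby ensuring 5 patients in each group at every increment of 10 enrollees". No stratification factor is named.
- **Primary analysis** (Statistical Analysis, Hypothesis 1a). A two-sided independent-sample t-test on the 12-month WOMAC, where "sample sizes of 37 and 37 achieve 81% power to detect a difference of 260 between the group means with standard deviations of 392" in each arm.
- **Where KL is used** (Statistical Analysis, Randomization). Two secondary analyses: one adds duration of symptoms, chondromalacia grade, KL and depression to the primary model, and the other uses propensity scores as weights. Because KL is added there, it is not in the primary model.

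**The concern.** The plan names one baseline factor that its own data suggest is prognostic, collects it before surgery, and admits patients on both sides of the pilot's split. It then uses the factor neither in allocation nor in the primary comparison. If KL does predict the 12-month WOMAC, its variation stays in the error term, and a chance KL imbalance between arms goes uncorrected in the primary result. With 37 completers per arm at a single site, precision is scarce. The secondary analyses do not recover it for the primary test, and the plan gives no rule for the case where adjusted and unadjusted results disagree.

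**Working it through.** **1. The plan's own power.** Inputs from Hypothesis 1a: difference 260, SD 392, 37 per arm, two-sided alpha 0.05.

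SE of the treatment difference = 392 × √(2/37) = 91 points. Power is 81.4% by the normal approximation and 80.4% by the noncentral t. The stated 81% reproduces. The noncentral t is used below.

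**2. The pilot KL gap.** Preliminary Studies gives the mean WOMAC improvement as 561 (95% CI 407-714) in all 45 patients and 656 (466-845) in grades 0-1. The number in grades 0-1 (n1) is not printed, so it is treated as an assumption.

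- SD of change, all patients: (714 − 407)/2 ÷ 2.015 × √45 = 511.
- Gap between grades 0-1 and 2-3: 656 − (45 × 561 − n1 × 656)/(45 − n1) = 4275/(45 − n1).
- At n1 = 29 the two subgroup SDs are nearly equal (498 and 503). The mean in grades 2-3 is then 389 and the gap 267.

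| Assumed n1 | Gap (points) |
|---|---|
| 20 | 171 |
| 25 | 214 |
| 29 | 267 |
| 30 | 285 |
| 33 | 356 |

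Sampling error at n1 = 29: SE = √(498²/29 + 503²/16) = 156. The 95% interval is 267 ± 2.017 × 156, about −48 to 582, which includes zero.

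**3. What a KL term would gain.** Assume one third of patients are KL 2, so KL contributes variance (1/3)(2/3) × gap² = (2/9) × gap². A gap of 140 is included as an assumption, roughly half of 285, because the pilot's worse group contained KL 3.

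If the gap carries over in full to 12-month scores, residual SD = √(392² − (2/9) × gap²):

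| Gap | Variance explained | Residual SD | SE of difference | Power |
|---|---|---|---|---|
| none used | 0 | 392 | 91 | 80.4% |
| 140 | 2.8% | 386 | 90 | 81.5% |
| 267 | 10.3% | 371 | 86 | 84.4% |
| 285 | 11.7% | 368 | 86 | 85.0% |

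That calculation sets a change-score gap against 392, which is the pilot's preoperative SD. If the explained share is instead taken on the change-score scale, (2/9) × gap²/511², it is 1.7% at 140 and 6.9% at 285. Power is then 81.0% and 83.1%.

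At the far end, a gap of 356 would give about 85% to 88% on the two scales. It requires pilot SDs as unequal as 534 and 334.

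**4. Chance imbalance.** The between-arm difference in KL 2 share has SD √(2 × (2/9)/37) = 0.110. With a gap of 285 this moves the treatment difference with an SD of 31 points, and by more than 61 points in 5% of trials. With a gap of 140 the figures are 15 and 30. This movement is already part of the SE of 91. Removing it gives the 86-90 above.

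**5. Interim look.** With about 10 per arm, crossing the 4.3326 boundary needs an observed difference of about 4.3326 × 392 × √(2/10) = 760 points. KL imbalance at a gap of 285 has an SD of √(2 × (2/9)/10) × 285 = 60 points.

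**The case against.** The strongest reply is that the KL effect is not established. The pilot prints no subgroup sizes and no direct test of grades 0-1 against 2-3. KL was singled out from several factors in 45 patients, which tends to exaggerate an effect. The worse group included KL 3, and the contrast is in change scores, while the primary outcome is the 12-month score and baseline by KL is not given. All of this stands, and it is why the gain is given as a range that starts near 1 percentage point.

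The plan also does not ignore KL. Two secondary analyses take it up, and the propensity-weighted one is offered as the answer to the power cost of adding many covariates. That is a fair defense against a charge of neglect. It does not improve the primary test, and a single KL term costs one degree of freedom, not the several that worry the plan.

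Allocation without KL strata is also legitimate. Randomization protects the comparison on average, and blocks of 10 deliver the equal numbers the plan wants, especially at the interim look. Stratified envelopes would weaken that balance, and the power gain computed here comes from the model term.

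**Conclusion.** The point holds as a modest loss of precision. Prespecifying one KL term would lower the SE of the primary treatment difference from 91 to about 86-90 points and raise power at 37 per arm from about 80% to about 81-85%. This assumes that one third of patients are KL 2, that the KL 0-1 versus KL 2 gap is 140 to 285 points, and that it carries over at least in part to 12-month scores. If the true gap is near zero, the term gains nothing and costs almost nothing.

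Three stronger readings are tempting, and the documents do not support them:

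- **That the pilot shows a KL gap as large as the 260-point target.** The point estimate is of that order, but it rests on an inferred subgroup size, its interval includes zero, and it concerns a different contrast and outcome scale.
- **That shifts of 31 or 61 points are bias or extra error.** They are ordinary sampling variation, already counted in the planned SE. The estimate is unbiased and alpha is held.
- **That KL imbalance could trigger an early stop.** A boundary of about 760 points makes this negligible.

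**What to change.** In Hypothesis 1a, replace the unadjusted t-test as the primary analysis with a linear model for the 12-month WOMAC containing treatment and one KL term (0-1 versus 2), graded from the preoperative radiograph and recorded before the envelope is opened. Keep the unadjusted t-test as a sensitivity analysis, state that the adjusted result is primary if the two differ, use the same model and boundary at the interim look, and include KL in the multiple imputation model.

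The cost is one model term and one degree of freedom, with no added patients, visits or procedures.

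Stratifying the envelopes by KL is optional. It needs a second envelope series and loses the exact 5:5 split per 10 enrollees. With two strata and blocks of at most 6, for example, arm totals could differ by up to 6, so the first 20 patients could split 13:7 at the interim look.

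### One fixed block size of 10, written in the protocol, would let anyone on the surgical side who tracks results know about 16% of assignments in advance; varying, undisclosed sizes of similar average would remove most of that

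*Combined protocol and SAP*

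**What the plan says.** All of this is in the combined protocol and SAP.

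- **Patient Selection** names a single source of patients: "Subjects will be recruited from the orthopedic clinic at the VA Palo Alto Healthcare System".
- **General Study Plan** says that eligible patients already scheduled for surgery "will be approached during their preoperative visit to participate in the study", and then: "They will be enrolled when they give informed consent". The baseline questionnaires, gait analysis, MRI and radiographs follow, all before surgery.
- **Evaluation at the time of surgery** gives the mechanism: "Randomization will be done by opening a sealed envelope in the operating room prior to the procedure". The block size is fixed ("randomization will be done by permuted blocks of size 10, thereby ensuring 5 patients in each group at every increment of 10 enrollees") and no strata are described. The reason given is "To ensure balanced numbers in the two surgical conditions, especially at the time of the interim look".
- The same section limits knowledge of the result after surgery: "All postoperative contact from this point forward will be made by study personnel who were not involved in the surgery". Patients are blinded too. Nothing comparable covers the people who operate or schedule.
- **Hypothesis 1a** sets the interim trigger: "The interim look will thus take place when the first 20 subjects (25% of the total 74) complete the 12 month assessment".

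The documents do not mention an independent holder of the list, numbered envelopes, or withholding of the block size from the surgical team.

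**The concern.** With a constant block size, a person who counts past results can work out the end of each block. Once five patients in a block have gone to one arm, the rest must go to the other. Counting would not be hard: 82 patients over months 2 to 32 of the timeline is 82/30 = 2.7 a month at one site.

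Selection bias needs two things: knowledge of the next assignment, and some freedom over which patient receives it. Blinding the patient and the follow-up staff addresses neither. A visible prognostic factor exists. In the pilot, patients with radiographic grade 0-1 improved more than those with grade 2-3, the trial admits grades up to 2, and radiographs are taken before surgery. The primary comparison is an unadjusted t-test on 12-month WOMAC, so a systematic difference in who goes next would pass straight into it, and a larger sample would not dilute it.

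The justification offered for the fixed block also needs a check. Blocks balance patients as they are randomized, whereas the interim look is triggered by patients who complete 12 months.

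**Working it through.** **Inputs.** Block of 10, 5 per arm (Evaluation at the time of surgery); 82 enrolled and 10% loss over one year (Hypothesis 1a); interim look at 20 completers (Hypothesis 1a).

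**The plan's own figure.** Five per arm in every ten is true by construction for patients *randomized*. The text says enrollees, but enrolment is at consent and randomization is at surgery, so the two sequences need not coincide.

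**Certainty under the fixed block.** Assignment k is certain when one arm already has its five. There are C(10,5) = 252 arrangements, and the probability is 2·C(k−1,5)/252:

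| Position | Probability of certainty |
|---|---|
| 1st-5th | 0 |
| 6th | 2/252 = 0.8% |
| 7th | 12/252 = 4.8% |
| 8th | 42/252 = 16.7% |
| 9th | 112/252 = 44.4% |
| 10th | 252/252 = 100% |

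The sum is 420/252 = 1.67 per block. Eighty-two patients fill eight blocks, and the last two open a ninth block in which neither can be certain. The total is 8 × 1.67 = 13.3 of 82, or 16.3%.

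**Guessing under the fixed block.** Always guessing the arm with more places left is right [5 + (2^10/252 − 1)/2]/10 = (5 + 1.53)/10 = 65.3% of the time in a full block, and 65.0% over 82 assignments.

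**Alternatives.** These are simulations of 82 assignments, for an observer who sees every result and knows which sizes are in use but not their order:

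| Block sizes | Certain | Likelier arm at 75% or more | Correct guesses | Largest running imbalance |
|---|---|---|---|---|
| 10 fixed | 16% | 23% | 65% | 5 |
| 4, 6, 8 | 2.4% | 35% | 68% | 4 |
| 8, 10, 12 | about 1.3% | 21% | 65% | 6 |

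Varying the size removes certainty. Making blocks smaller on average gives part of the gain back, because guessing improves.

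**Possible size of bias.** The documents give no figure, so this rests on an assumption: patients placed in a slot known to be one arm differ by h WOMAC points from average, with opposite signs for the two arms. If only the certain slots are steered, the arm means differ by 2 × 0.163 × h = 0.33h. For h from 25 to 100 that is 8 to 33 points, against a target difference of 260 and a non-inferiority margin of 194. If every slot were steered by best guess, the figure would be 2 × (2 × 0.653 − 1) × h = 0.61h, or 15 to 61 points.

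**Interim balance.** With 10% loss, 20 completers come from about 20/0.9 = 22 patients, which is not two whole blocks. Simulating blocks of 10 with independent loss, equal in both arms, and taking the first 20 completers gives:

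- exactly 10:10 in 48%
- 11:9 or worse in 52%
- 12:8 or worse in 9%
- 13:7 or worse in 0.8%

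The chance of exactly 10:10 is 65% at 5% loss and 35% at 20% loss. The standard error of the difference, √(1/a + 1/b) relative to 10:10, rises by 0.5% at 11:9, 2.1% at 12:8 and 4.8% at 13:7.

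**The case against.** The strongest reply is that the route to bias is narrow and partly inferred. Eligibility, consent and all baseline measures come before the envelope, so the entry criteria that need judgement are settled by then. To invite by arm, a recruiter would have to foresee the block position on a later surgery date. The documents do not say how many surgeons operate, who holds or logs the envelopes, or who orders the list. The figure of about 100 waiting patients is given only for recruitment feasibility and covers knee arthroscopy generally. All of this stands. It leaves the order or timing of surgery near a block's end as the main route, with choice of whom to approach a weaker one.

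A second reply is that the Randomization paragraph of the Statistical Analysis plans secondary analyses adjusting for symptom duration, chondromalacia grade, Kellgren-Lawrence grade and depression, and a propensity-weighted analysis. Hypothesis 1a adds change-score sensitivity analyses. These help with measured factors. They are not the primary test, and they cannot correct selection on anything unrecorded.

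A third reply is that ten is already a large block and that common smaller mixtures make guessing easier. This is correct for sizes 4, 6 and 8, and it determines the choice of sizes in the fix.

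Finally, interim imbalance has no material consequence for the test. That also stands.

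**Conclusion.** The predictability is real and should be removed, because doing so is cheap. About 13 of 82 assignments (16%) would be known with certainty, and 65% guessed correctly, by someone who knows the block size and sees every result. That such a person exists is the natural reading at one clinic with envelopes opened in the operating room, but it is an assumption.

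A reader might infer more than the documents support:

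- *Upcoming assignments in general can be deduced.* They cannot. The first five in a block are never certain, and certainty is concentrated in the ninth and tenth.
- *The surgical team is known to see every result and to choose the order.* Neither is stated.
- *The block size was public during recruitment.* It is written in the protocol; the documents do not show who had access to it while patients were being enrolled.
- *The interim analysis is compromised.* It is not. The balance claim is inaccurate for completers, but the usual imbalance costs 0.5% to 2.1% in standard error.

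The size of any bias in WOMAC is unknown. The 8 to 33 points shown depend wholly on the assumed h.

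**What to change.** 1. In Evaluation at the time of surgery, replace the fixed block of 10 with permuted blocks whose size varies at random and is not smaller on average, for example 8, 10 and 12. Do not use 4, 6 and 8, which raise correct guessing to about 68%.
2. Keep the sizes out of any document that the surgical team sees.
3. State that the list and sequentially numbered envelopes are prepared by existing staff outside the surgical team.
4. Reword the interim rationale to say that blocking keeps the numbers randomized close to equal, and that the first 20 patients to complete 12 months may not split evenly. Refer to patients randomized where the text now refers to enrollees.

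The cost is a new list before the first patient is randomized and a few sentences in the protocol. The largest running imbalance rises from 5 to 6, with negligible effect on precision. Guessing stays at about 65%, so the gain is the fall in certainty from about 16% to about 1%, not full unpredictability.
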